In view of the limitations of an exercise alone programme, a pilot study was conducted to evaluate the preliminary effects of using an exercise programme plus the implementation of face-to-face behavioural change techniques (BCT). Eighty-five frail older people were randomly assigned to either the exercise

combined with BCT intervention (COMB), exercise only (EXER), or usual care (control) groups (Liu et al., 2017). Feasibility was achievable with high recruitment (87.2%) and low overall attrition (7.1%) rates. With the exception of the attendance rate and the self-perceived exercise compliance scores, we found no statistically significant differences in the other outcome assessments due to the small sample size in the pilot study. However, participants in the COMB group reported that ‘goal setting’ and ‘obtaining encouragement and suggestions from the BCT facilitator’ were the most effective ways of increasing their confidence in adhering to the exercise regimen. This pilot study showed that the combined exercise training and face-to-face BCT programme has the potential to strengthen the participants’ engagement in daily exercises, as reflected by their significantly higher self-reported exercise compliance and higher attendance rate in all of the training sessions during the 12-week programme [$F(2,76) = 5.64, p < 0.01$] when compared with the other two groups. Not surprisingly then, a trend of greater improvement in physical endurance was observed in the COMB group than in the other two groups, although the figures did not reach statistical significance because of the small sample size. However, one drawback is that the effects of implementing face-to-face BCT are likely to gradually fade after the programme.

Rationale for combining exercise training with a wearable activity tracker (WAT)-based intervention to increase physical activity levels in frail older people

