Although the ultimate goal of using WATs should be increased MVPA, such data was not reported in previous studies on older people. Moreover, the suggested additional measures for facilitating the adoption of WATs by older people have not previously been tested. It is worth testing the efficacy of a combined intervention of exercise training plus WAT intervention in which BCTs have been incorporated. Little is presently known about the efficacy of using a WAT intervention among older people with frailty. The main hypothesis is that the WAT intervention plus exercise training programme will increase physical activity levels compared to an exercise programme alone. If we are successful in proving the hypothesis, we will propose studying the long-term effects (i.e., increased daily MVPA and the adoption of a physically active lifestyle) of this intervention in the main study with a larger sample size with a longer follow-up period.

B. Research plan and methodology (Appendix 1: Consort Research Flowchart)

Aim: A single-blinded, repeated-measures, two-arm pilot cluster RCT is proposed to examine the feasibility and preliminary effects of an exercise programme with or without a WAT intervention for promoting physical activity levels among community-dwelling older people with frailty. To explore the acceptability of the WAT intervention, a focus group with all participants in the experimental group (4-6 people per group) will be interviewed by JS (the Co-I).

Subjects and Settings: A district community health centre will be viewed as one unit/cluster. Eligibility criteria for district community health centres are those that are funded by the Hong Kong (HK) government and under the supervision of the Social and Welfare Department of HK, and thus that meet a specific set of standard regulations and criteria on environment and practices. Six community centres, which provide similar types of community care and social support services for community-dwelling older people, will be invited by a convenience method to work as collaborators in this study. The target population of this study are community-dwelling older people with frailty who will be recruited through the community centres.

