Sample size: Teare et al., 2014 recommended that a pilot study is required a total number of participants between 60 and 100 when estimating the effect size for a continuous outcome. Thus, sixty participants will be recruited from six community centres. We estimate that about 25-50% of the members of these centres will be eligible to participate (Schultz-Larsen et al., 2007; Liu, 2017). We will target moderate to large centres with the total number of centre members around 800. Given that we can screen 200 older people (50 in each centre) per 4 to 6 weeks, and based on our previous study in similar centres (Liu et al., 2017), we believe that we will need about 3 to 4 months to recruit 60 participants (with 30 subjects recruited per 4 to 6 weeks in two-three centres) for this study. Given the difficulty of obtaining details of the backgrounds of all potential participants in these community settings, a properly random sample cannot be implemented. Thus, convenience sampling will be used to recruit participants among the collaborative community centres. Using computer-generated random numbers, a biostatistician not affiliated with this study will randomize the centres in a 1:1 ratio into either: the control or the experimental groups. Participants from each centre will be placed in their centre's corresponding group to avoid 'contamination' effects across participants. To avoid selection biases, the allocation to the study groups will be concealed from the researchers until sample recruitment and baseline measurements have been completed. Appendices 1 and 2 show the CONSORT research flow chart and the timeline of this study.

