The Control Condition: The same physical training and BCTs support will be arranged for the control group.

Instruments and Measures:

Participants will be assessed on a variety of outcomes (described below) at 1 week and at 1 and 3 months (T1 – T3) after the programme, which will be compared with the baseline assessment (T0). The participants will be asked to wear an ActiGraph Wgt3x accelerometer on their non-dominant wrist for 7 days before the commencement of any intervention, as well as during each outcome assessment time point.

Socio-demographic data: The following data will be collected: 1) data on age, gender, marital status, exercise habits, living conditions, and level of education, 2) the participants' health-related information, including their morbidities, cognitive status, medications, and number of hospital and out-patient clinic visits in the past 12 months.

Feasibility:

To understand the feasibility of this intervention, the frequency with which the participants in the experimental group use the tracker over the time of the study (i.e., 112 days), the recruitment rate, the attrition rate, the participants' adherence to the exercise regimen, and reports of adverse effects will be monitored.

Primary outcome measurement: Activity levels

The participants' physical activities and sedentary time will be objectively measured using a ActiGraph wGT3X accelerometer.

Secondary outcome measurements

Fitbit Data (only participants in the experimental group): The total steps per week, total walking distance per week, and time spent in different heart rate zones (50-69%, 70-84%, and >85% of the maximum heart rate) of an individual will be collected.

Physical Endurance: This will be evaluated using different physical tests:

1. The participants' lower-limb muscle and upper-limb strength will be assessed using a 30-second chair stand test and a handheld Jamar Hydraulic Hand Dynamometer, respectively.
2. Mobility will be assessed through the Timed-up-and-Go (TUG) test and by their gait speed (2-m walk). These two tests assess the overall performance of the lower limbs and walking speed, which can reflect the effect of exercise in enhancing the participants' overall physical endurance.

Exercise Self-efficacy: The participants' self-confidence in their ability to exercise in a variety of circumstances (e.g., even when they were feeling tired) will be assessed using the Chinese Self-Efficacy for Exercise scale (CSEE).

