Official Title: Enhancing physical activity levels of community-dwelling older people with frailty through an exercise intervention with or without a wearable activity tracker (WAT)-based intervention: a feasibility and pilot study

Date of the document: 22/03/2018

Approved by the Human Subjects Ethics Sub-committee of The Hong Kong Polytechnic University on 13/04/2018

Statistical Analysis:

SPSS version 23.0 will be used to analyse the data. Descriptive statistics will be generated for the demographic data and feasibility tests. The baseline characteristics of the participants in the two groups from the six community centres will be compared using unpaired t test for the continuous variables, a chi-square test for the categorical variables, and the Mann-Whitney U test for the ordinal variables. Normality assumptions for the variables will be examined by a K-S test. The group attendance and drop-out rate of the participants in the study groups will be reported. An intention-to-treat analysis will be adopted. An independent sample Student's t-test or Mann-Whitney U test will be used to examine differences between the control and experimental groups in the outcome variables. For categorical and dichotomous outcome variables, an χ^2 test will be used to test differences between the groups. If significant differences between the groups at baseline have been identified, these data will be treated as covariates and adjusted for as needed. A p-value of < 0.05 will be considered statistically significant. ANOVA will be used to measure the effectiveness of the intervention. If the data were non-normal, Friedman's test will be used instead. Post-hoc within-group comparisons will be done using paired t-tests or Wilcoxon's signed rank test, and Bonferroni adjustments will be made.

Content analysis will be used to analyse the interview data. All audio-taped interviews will be transcribed into Cantonese by the RA and the transcriptions will be checked for accuracy by two members of the research team before the analysis.

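### The tests that follow the effectiveness ANOVA are within-arm only, and the SAP does not name the between-arm contrast that decides the tracker question

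*SAP*

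**What the plan says.** The Protocol (A. Background, last paragraph) puts the question between arms: "The main hypothesis is that the WAT intervention plus exercise training programme will increase physical activity levels compared to an exercise programme alone". Under The Control Condition it adds: "The same physical training and BCTs support will be arranged for the control group". Outcomes are taken at T0 and at three visits after the programme (T1 to T3), each to be compared with T0 (Instruments and Measures; Procedures).

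The SAP has one Statistical Analysis section. In order, the parts that matter here are:

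- independent t or Mann-Whitney tests, and chi-square tests for categorical outcomes, between the two groups, with adjustment for variables that differ at baseline;
- the threshold: "A p-value of < 0.05 will be considered statistically significant";
- an ANOVA as the measure of effectiveness, with Friedman's test as the non-normal alternative;
- the follow-up step: "Post-hoc within-group comparisons will be done using paired t-tests", or Wilcoxon signed-rank tests, with Bonferroni adjustment.

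The ANOVA's factors are not listed and no group-by-time term is named.

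**The concern.** The tests placed after the effectiveness analysis, which are also the only tests with a multiplicity adjustment, ask whether each arm changed from its own baseline. The hypothesis asks whether the arms changed by different amounts.

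The gap matters more here because the control arm is active. Both arms may improve through the exercise itself or through practice with the tests. Regression to the mean may add to this, because entry can rest on low grip strength, slow gait or a low PASE-C score. With a moderate common gain and about 30 people per arm, chance alone can put one paired test below the threshold and leave the other above it. That pattern is easily read as the tracker working, or as the tracker doing harm, when the true difference is zero.

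The between-group tests in the SAP could guard against this. However, the SAP does not say at which visit they apply, whether they use change or raw scores, or that they take precedence. On the non-normal route, Friedman's test compares time points and has no group factor.

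**Working it through.** **The plan's own figures.** "Thus, sixty participants will be recruited from six community centres", and a biostatistician will "randomize the centres in a 1:1 ratio into either: the control or the experimental groups". So 60/2 = 30 per arm and 60/6 = 10 per centre. The 60 comes from a recommended pilot range, not from a power calculation, so there is no stated effect size, SD or power to reproduce.

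**Assumptions (not in the documents).** Two-sided tests; the same true gain in both arms, in units of the between-person SD; correlation r = 0.7 between T0 and each visit; Bonferroni over three comparisons with T0 (0.05/3 = 0.0167), since the SAP does not give the number; participants independent; paired tests run whatever the ANOVA shows.

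**Formulae.** SD of change = √(2(1 − r)) = √0.6 = 0.775. Standardised gain dz = gain/0.775. Power p of each paired t-test comes from the noncentral t with 29 degrees of freedom and noncentrality dz × √30. With independent arms and equal gains, P(exactly one arm significant) = 2p(1 − p), and P(tracker arm only) = p(1 − p).

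**Example, gain 0.3 SD.** dz = 0.387, noncentrality 2.12, p = 0.353; 2 × 0.353 × 0.647 = 0.457.

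| Common gain (SD) | dz | p | Exactly one arm | Tracker arm only |
|---|---|---|---|---|
| 0 | 0 | 0.017 | 3.3% | 1.6% |
| 0.1 | 0.129 | 0.044 | 8.4% | 4.2% |
| 0.2 | 0.258 | 0.147 | 25% | 13% |
| 0.3 | 0.387 | 0.353 | 46% | 23% |
| 0.4 | 0.516 | 0.616 | 47% | 24% |
| 0.5 | 0.645 | 0.833 | 28% | 14% |
| 0.6 | 0.775 | 0.949 | 9.7% | 4.8% |
| 0.8 | 1.033 | 0.9985 | 0.3% | 0.15% |

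**Ceiling.** 2p(1 − p) cannot exceed 50%, reached at p = 0.5. With 30 per arm that is dz = 0.37 without adjustment, 0.46 with Bonferroni for 3 and 0.51 with Bonferroni for 6. Bonferroni therefore moves the peak and does not lower it. With 28 per arm (about the 7.1% attrition of the earlier pilot) the peaks are at 0.38, 0.48 and 0.53.

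**Sensitivity to r.** At r = 0.5, gains of 0.3 and 0.4 SD give 32% and 47%. At r = 0.9 they give 24% and 2%.

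**Any of the three visits.** By simulation (20,000 trials, r = 0.7, equal correlation among all four visits), exactly one arm is significant at one or more visits in about 50%, 79%, 81% and 55% of trials for gains of 0.2, 0.3, 0.4 and 0.5 SD.

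**Effect of a gate.** If the paired tests were run only after a significant group-by-time term, a discordant result would pass in about 3% of trials at one visit and 4-5% at any visit, for gains of 0.2 to 0.5 SD. If the gate were the overall time effect, which equal gains trigger, the any-visit figures at 0.3 and 0.4 SD stay at about 75% and 80%.

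**The direct test.** An independent t-test on change at one visit is falsely significant in about 5% of these trials, whatever the common gain. Centres are randomised, though. With an assumed ICC of 0.05 for change, the design effect is 1 + 9 × 0.05 = 1.45, and the same unclustered test is falsely significant in about 10-11%.

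**The case against.** The strongest answer is that the SAP does contain between-arm tests. A reader who sees only the post-hoc sentence might infer that the tracker question rests on within-arm tests alone. The documents do not support that: t, Mann-Whitney and chi-square tests between groups are planned in the same section. What remains is that their visit, scale and standing are not stated, and that they are not tied to the ANOVA.

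Second, a reader might infer that the sponsor plans to claim an effect when one arm is significant and the other is not. Nothing in the SAP says so. It assigns effectiveness to the ANOVA, and the Protocol's plan to compare each visit with baseline gives the paired tests a legitimate descriptive use. This objection stands in full.

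Third, it is tempting to say that about half of trials would show a discordant result. That figure holds only near 50% within-arm power. The documents give no effect size, SD or correlation that would place this trial there, and the rate runs from under 1% to 50%.

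Fourth, post-hoc tests are usually run after a significant omnibus test. A group-by-time gate would remove most of the problem, but the SAP states neither the term nor the gate, and Friedman's test cannot supply one.

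Finally, this is a feasibility pilot, so the consequences are limited. But the sample size is justified by a source cited on what is needed "a pilot study is required a total number of participants between 60 and 100 when estimating the effect size for a continuous outcome", and that purpose is served by a between-arm estimate, not by two within-arm p-values.

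**Conclusion.** The point holds as a gap in the specification. The hypothesis is between arms; the only tests placed after the effectiveness ANOVA, and the only ones adjusted for multiplicity, are within arms; and no between-arm contrast of change is named as decisive.

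If the within-arm results were read as a comparison, equal true gains would give significance in exactly one arm at a given visit in about 3% to 47% of trials for gains from 0 to 0.4 SD, falling to under 1% at 0.8 SD. At most 25% per visit would wrongly favour the tracker. These rates depend on the assumed gain, correlation and Bonferroni divisor, on independence of participants, and on the absence of a group-by-time gate.

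It is a risk of misinterpretation. It does not show that the plan lacks between-group testing or commits the sponsor to a wrong inference. It should be corrected, since the correction needs only SAP wording.

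**What to change.** Replace the post-hoc sentence in the SAP with:

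> Follow-up comparisons will be the between-arm differences in change from T0 at T1, T2 and T3, with 95% CIs, Bonferroni-adjusted over the three visits, from a model with a group-by-time term that allows for centre. These contrasts are the between-group tests of the outcome variables and decide the tracker question. Within-arm changes will be reported descriptively (mean change and CI), and no conclusion about the tracker will be drawn from them.

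This ties the existing between-group tests to one contrast, and it states the group-by-time term that the ANOVA sentence leaves open.

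The cost is SAP wording, the loss of the within-arm p-values, and wider intervals. As an illustration, an analysis on centre means has 6 − 2 = 4 degrees of freedom, so the 95% multiplier is 2.78 instead of 2.00 with 58, about 1.39 times as wide before any clustering is counted. At the assumed ICC of 0.05, clustering adds a further factor of √1.45 = 1.20. That width reflects what six randomised centres can show.
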